two cervical epidural steroid injections would be very appropriate in the treatment of a specific episode of cervical radicular pain. This literature also suggests that a maximum of four injections can be used within six months, assuming there was a positive response and improvement seen with the previous injections.

Study Design

This is a randomized, double-blinded clinical trial. The total enrollment goal is 60 patients (30 per treatment group)

Objective

The purpose of this study is to determine the effectiveness of cervical transforaminal epidural steroid injections in decreasing the need for an operation in patients with cervical radicular pain, otherwise considered to be operative candidates.

Treatment Groups:

Patients will be randomized in a 1:1 fashion to one of the following treatment arms:

1. Cervical transforaminal injection: 1.0 cc Lidocaine 1.0% with 1.0 cc normal saline
2. Cervical transforaminal injection: 1.0 cc Lidocaine 1.0% with 1.0 cc of Dexamethasone (10 mg/cc)

Primary/Secondary Outcome Variables

Primary Outcome Variables: The primary outcome variable is the avoidance of surgery. Treatment success is defined as the avoidance of surgery, while treatment failure is defined as having surgery due to failure of the injection treatment to alleviate pain and improve function over the 12 months they are being followed for purposes of this study.

Secondary Outcome Variables: Secondary outcome variables include:

- Decreased disability as measured by the validated outcome measure tool, the Neck Disability Index (NDI).
- Decreased neck pain and radicular pain as measured by a numerical pain rating, Verbal Numeric Pain Score with 0 being no pain and 10 being the worst pain imaginable
- Patient Satisfaction as measured by a numerical pain rating, Verbal Numeric Pain Score with 0 being completely unsatisfied and 100 completely satisfied

Patient Selection and Treatment Plan

Patients deemed to be surgical candidates for the treatment of cervical radicular pain at OrthoCarolina, PA will be screened for eligibility and asked to participate in the study. Potential subjects will meet with a research coordinator to discuss the details of the study. Those who choose to participate will be consented accordingly.

Inclusion Criteria:

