Study patients can elect to abandon the injection treatment and elect to undergo surgical treatment at any point during the course of the study. It is defined as treatment failure if a study patient elects to undergo surgical treatment. Patients who elect to undergo surgery will be discontinued from the study and no further effectiveness evaluations will be performed. Patients, referring physicians, and evaluating physician assistants are blinded to the treatment group. The treating physiatrist will not be blinded to the medications but will not be performing any clinical follow-up exams.

Follow-up Office Visits

Patients will be asked to return to the clinic 4 weeks, 12 weeks, 6 months, 12 months (following their first injection date) and the following data points will be collected for both groups:

- NDI questionnaire (disease specific measure), Verbal Numeric Pain Score, Blinding Assessment (patient and investigator), Pain Medication Use, Neurological Exam, and Subject satisfaction.

In the event that the patient receives their second, third, or fourth injection within 1 week prior to one of their follow-up office visits, the post injection phone call data will be collected at that visit. The study coordinator will tell the subject their baseline, pre-procedure Verbal Numeric Pain Rating and ask the subject to rate their current radicular pain intensity. Patients will also be asked to rate their overall satisfaction with their treatment and their current narcotic medication use.

The full schedule of assessments is shown in study flow chart below.

Study Flow Chart:

Study procedure	Screening	0 (day of procedure, injection #1)	Phone Call	Injection #2 (At least 14-21 days after #1)	4 weeks post injection	12 weeks post injection	6 months post injection	12 months post injection
Informed Consent	x							
Inclusion/Exclusion	x							
Verbal Numeric Pain Score**	x		x		x	x	x	x
NDI	x				x	x	x	x
Neuro Exam	x				x	x	x	x
Injection*		x		x				
Blinding Assessment - Patient					x	x	x	x
Blinding Assessment - Investigator					x	x	x	x
Pain Medication Use	x	x	x	x	x	x	x	x
Subject satisfaction			x		x	x	x	x
Adverse Events			x	x	x	x	x	x

* Patients may receive up to four injections within the 12 month period. Injections will be scheduled at least 14 days apart.

** Patients will be called one week after injection 1, 3 (as needed), and 4 (as needed)

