***If an injection occurs within 1 week prior to follow-up visits, patient will not be called. Verbal Numeric Pain Scale, Pain Medication Use, Subject Satisfaction and Adverse Events will be recorded during the follow-up visit.

Unblinding Procedures

Patients will not be unblinded to their study treatment. Unblinding of patients will only occur by the data manager and statisticians in the event of an SAE that is deemed possibly or probably related. Subjects that have been “blind-broken” must be discontinued from the study and no further effectiveness evaluations will be performed. However, the SAE will continue to be followed up until resolution.

Sample Size

Sample size calculations are based on the study by Riew et al. (2000). We estimate that 30% patients randomized to Lidocaine will avoid surgery compared to 70% of the patients randomized to Lidocaine with Dexamethasone. With a level of significance of 0.05 and power of 80%, 23 patients are needed in each group. To account for a 30% attrition rate, 30 patients are needed in each group. The total enrollment goal is 60 patients.

Risks

As with all medications, side effects may include an allergic reaction. Allergic reactions may range from minor reactions, such as itching or rash, to major, life-threatening reactions which can result in death.

Risks associated with cervical transforaminal injections include, but are not limited to:

Likely

- Spinal headache;

Less Likely

- Nerve irritation;
- Nerve injury;
- The risk of bleeding and/or infection into the spinal area;
- Reaction to medications;

Rare, but Serious

- Lung collapse;
- Seizures
- Paralysis
- Loss of vision
- Stroke
- Death.

Risks of general anesthesia or moderate sedation include, but are not limited to:

The most common side effects may include:

- Headache
- Adverse reaction to medications

Less common side effects of may include:

- Bleeding sufficient to cause anemia or require transfusion
- Hematoma (bleeding from the procedure)
- Pseudoaneurysm (injury to a blood vessel)
- Seroma (a collection of fluid under the skin)
- Blood vessel injury
- Pneumonia

Rarely, side effects may include:

- Hypotension (drop in blood pressure)
- Cardiopulmonary arrest (heart attack)
- Stroke
- Pulmonary embolism (a blood clot to your lungs)

- Death

Risks associated with contrast agents that are used in the procedure include, but are not limited to:

- Allergic reaction
- Anaphylaxis
- Death

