Normality testing will be conducted for all continuous variables. Standard descriptive statistics will be calculated for patient demographic variables as well as the primary and secondary outcome variables. For variables measure at the ordinal level (i.e. categorical data) frequencies and percentages will be reported. Mean and standard deviation will be reported for all normally distributed data measured as intervals or ratios (i.e. continuous data). Median and interquartile range will be reported for continuous variables that are skewed. The incidence of surgery avoidance will be calculated. Bivariate analyses will be conducted to determine the associations between surgery avoidance and age, gender, pain, function, pain medicine consumption, BMI and subject satisfaction. Chi-Square tests will be used for categorical data and t-test or the nonparametric equivalent will be used for continuous data.

Adverse Event Reporting

Adverse events such as, death or any other complication will be reported to the IRB.

Subjects will be instructed to report any "Serious Adverse Event" immediately to the investigator.

"Serious Adverse Event" is defined as any event that:

- Results in death
- Is life-threatening
- Results in persistent or significant disabling/incapacity
- Requires inpatient hospitalization or prolongation of hospitalization
- Is a congenital abnormality/birth defect
- Requires medical or surgical intervention to prevent permanent impairment or damage

Serious adverse events will be reported to Presbyterian Healthcare Institutional Review Board within 24 hours of the event. This report may be done by phone initially and will follow with an adverse event report form.

Data Safety Monitoring

A Data Safety Monitoring Board will review data for integrity.

[name]., Chairman, Research Committee will serve as the safety monitor. A data safety monitoring board (DSMB) will review data on a bi-monthly basis or as needed. The DSMB are members of the OrthoCarolina Research Institute (OCRI) Research Advisory Committee.

Data Safety Monitoring Plan

Serious adverse events (SAEs) that are "related," "probably related" or have an "unknown" relatedness to the study procedure, will be reported to the data safety monitoring board via email as they occur. The data safety monitoring board meets every

other month. At each meeting the study will be reviewed for adverse events, serious adverse events, and overall feasibility issues.

Ethical and Regulatory Considerations

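### No rule keeps or counts 12-month surgery status for patients who are blind-broken, withdrawn or lost, and the between-arm test of surgery avoidance is implied but not written

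*Combined protocol and SAP*

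**What the plan says.** The Objective section sets a comparative question: "The purpose of this study is to determine the effectiveness of cervical transforaminal epidural steroid injections in decreasing the need for an operation". The Sample Size section is built on the same comparison: "We estimate that 30% patients randomized to Lidocaine will avoid surgery compared to 70% of the patients randomized to Lidocaine with Dexamethasone". It takes a significance level of 0.05 and 80% power, arrives at 23 per group, and enrols 30 per group to allow for 30% attrition.

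The Statistical analysis section then says that the incidence of surgery avoidance will be calculated, and continues: "Bivariate analyses will be conducted to determine the associations between surgery avoidance and age, gender, pain, function, pain medicine consumption, BMI and subject satisfaction". It assigns chi-square tests to categorical data and t-tests or a nonparametric equivalent to continuous data. It does not mention treatment arm, an effect estimate, a confidence interval or an analysis set.

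On outcome status, the section on third and fourth injections gives one rule: "It is defined as treatment failure if a study patient elects to undergo surgical treatment". The Primary Outcome Variables text is narrower, because it ties failure to surgery that follows from the injection not relieving pain and improving function.

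Under Unblinding Procedures, the blind may be broken "in the event of an SAE that is deemed possibly or probably related". Such patients "must be discontinued from the study and no further effectiveness evaluations will be performed". The text adds: "However, the SAE will continue to be followed up until resolution". The section on Withdrawal and Premature Discontinuation lets patients leave by their own choice or at the investigator's discretion. It gives no outcome rule for them.

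**The concern.** Two things are open for the primary endpoint.

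The first is the analysis itself. The listed associations describe which patients avoid surgery, not whether the steroid arm avoids it more often. The arm comparison has to be inferred, and its analysis set, effect measure and use of a continuity correction could be settled after the data are seen.

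The second is more important. A patient who withdraws, is lost or is blind-broken may have surgery before month 12 without the trial recording it. For blind-broken patients the protocol itself ends effectiveness evaluation, and the trigger is an event judged possibly or probably related. That reason is linked to treatment, so the loss cannot be assumed to be random, and it can bias the comparison of the arms.

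The documents also allow two conflicting readings of an unknown status. If success means avoiding surgery, anyone without a recorded operation might count as a success. The attrition allowance suggests instead that such patients drop out of the analysis. Neither reading is stated as the rule.

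**Working it through.** **Inputs.** From Sample Size: avoidance rates 0.30 (lidocaine) and 0.70 (lidocaine with dexamethasone), significance level 0.05, power 80%, 23 evaluable and 30 enrolled per arm, attrition 30%. Assumed here: a two-sided test, because sidedness is not stated; the same unknown share *u* in both arms; and avoidance rates of 0.30 and 0.70 among patients with known status.

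**The plan's own figure.** The pooled two-sided formula without continuity correction is

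n = [1.96 × √(2 × 0.5 × 0.5) + 0.8416 × √(0.3 × 0.7 + 0.7 × 0.3)]² / 0.40² = (1.386 + 0.545)² / 0.16 = 23.3.

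Exact enumeration of all 2×2 tables gives the uncorrected chi-square test 80.9% power at 23 per arm, so the stated 23 is reproduced. The attrition step is reproduced as 23 × 1.3 = 29.9, rounded up to 30. If 30% of 30 are in fact lost, 30 × 0.7 = 21 per arm remain.

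**Power by number with known status** (exact, uncorrected chi-square, two-sided 5%, 0.30 vs 0.70):

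| Known per arm | Unknown share of 30 | Power |
|---|---|---|
| 30 | 0% | 89.6% |
| 27 | 10% | 84.0% |
| 21 | 30% | 74.8% |

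**Bounds on the difference.** Known patients contribute 0.30(1 − u) and 0.70(1 − u) of each arm as avoided. In the worst case for dexamethasone, every unknown lidocaine patient avoided surgery and every unknown dexamethasone patient had it. The best case is the reverse.

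- Worst = 0.70(1 − u) − [0.30(1 − u) + u] = 0.40(1 − u) − u
- Best = [0.70(1 − u) + u] − 0.30(1 − u) = 0.40(1 − u) + u

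| u per arm | Worst | Best |
|---|---|---|
| 10% | 0.36 − 0.10 = +26 points | 0.36 + 0.10 = +46 points |
| 20% | 0.32 − 0.20 = +12 points | 0.32 + 0.20 = +52 points |
| 30% | 0.28 − 0.30 = −2 points | 0.28 + 0.30 = +58 points |

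**What the choice of rule can do.** As an invented example, take 21 known per arm, with 7 and 14 avoiding surgery and 9 unknown in each arm (uncorrected chi-square).

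- Known status only, 7/21 vs 14/21: χ² = 42 × (7 × 7 − 14 × 14)² / 21⁴ = 4.67, p = 0.031.
- Unknowns all failures, 7/30 vs 14/30: χ² = 60 × (7 × 16 − 23 × 14)² / (30 × 30 × 21 × 39) = 3.59, p = 0.058.
- Unknowns all successes, 16/30 vs 23/30: p = 0.058.
- Worst case, 16/30 vs 14/30: difference −6.7 points, p = 0.61.
- Best case, 7/30 vs 23/30: difference +53 points, p < 0.001.

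The same observed data fall on either side of 0.05 depending on a rule that the plan does not give.

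**The case against.** The strongest reply is that the comparison is not in real doubt. The protocol has two randomized arms, a binary primary outcome, a 12-month window, a sample size set on the difference between arms, and a sentence assigning chi-square tests to categorical data. This stands. A reader might infer that the trial has no primary analysis, or that it cannot answer its question. The documents do not support that; the arm test is under-specified rather than absent. The naming of chi-square also largely settles the choice against an exact test and leaves mainly the continuity correction open (89.6% power without it and 83.8% with it, at 30 per arm).

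A reader might also infer that patients who have surgery lose their primary outcome, because "Patients who elect to undergo surgery will be discontinued from the study and no further effectiveness evaluations will be performed". They do not, since elected surgery is itself counted as failure. What is unsettled for them is only that the two definitions of failure differ in scope.

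On blind-broken patients, the reply is that there may be very few or none. No expected number is given, and the most serious procedure risks are listed as rare. Both arms also undergo the same procedure, so related events need not differ by arm. This limits the size of the bias but does not remove its source, and the same missing rule covers all withdrawn and lost patients.

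Finally, the widest bounds need all of the 30% attrition to have unknown surgery status, with opposite extreme outcomes in the two arms. That is correct. They are limits, not a forecast.

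**Conclusion.** The point holds in this form. The plan does not say that 12-month surgery status is sought after a patient stops visits, does not say how an unknown status counts, and for blind-broken patients stops effectiveness evaluation for a treatment-linked reason. Not writing the arm comparison is a lesser gap, close to missing detail, but it should be closed at the same time.

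The size depends on a share of unknowns that the documents do not give. Across the assumed range of 10% to 30% per arm, the bounds on the expected 40-point difference widen from +26 to +46 points, out to −2 to +58. Power on known status falls from 84.0% to 74.8%, against 89.6% with complete status. The power figures assume equal unknown shares and that unknown patients resemble known patients in the same arm; the bounds give every unknown patient the extreme outcome. Nothing here shows that the result will be biased. It shows that the plan leaves open a bias that is cheap to prevent.

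**What to change.** 1. **Unblinding Procedures.** Amend the text so that stopping effectiveness evaluations does not extend to surgery status. Otherwise the new sentence would contradict the current one. Suggested wording: *For every randomized patient who stops visits, including blind-broken patients, 12-month surgery status is still sought by record check or phone call unless the patient refuses.* This changes data collection only; the rule on discontinuing patients is untouched.

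2. **Statistical analysis.** Add: *Primary analysis: surgery avoidance through 12 months is compared between arms as assigned, in all randomized patients with known 12-month surgery status, by a two-sided 5% Pearson chi-square test without continuity correction, with the risk difference and 95% CI. Sensitivity analyses include all randomized patients and count unknowns as all failures, all successes, best case and worst case.* Label the seven listed associations exploratory.

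3. **Definition of failure.** Reconcile the Primary Outcome Variables text (surgery because the injection treatment failed) with the later rule (any elected surgery), so that the endpoint has one definition before analysis.

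**Cost.** A few sentences, and a record check or phone call for patients who stop visits. Serious adverse events are already followed to resolution, so contact with blind-broken patients continues at least until then. The Risks section describes record use for medical history, so the IRB submission or consent form may need one added line. The primary analysis still assumes that any remaining unknowns resemble known patients in the same arm; the sensitivity analyses show how far the result depends on that.

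### The tests of association with surgery avoidance leave out randomized arm, so for variables measured after injection they mix the treatment effect with any patient-level link

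*Combined protocol and SAP*

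**What the plan says.** The Statistical analysis section plans this: "Bivariate analyses will be conducted to determine the associations between surgery avoidance and age, gender, pain, function, pain medicine consumption, BMI and subject satisfaction". It names chi-square tests for categorical data, and a t-test or nonparametric equivalent for continuous data. It mentions no adjustment for arm and no stratification by arm. It does not say in words that the arms are pooled, but no by-arm analysis is described, so pooling is the natural reading.

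The section gives no time point for pain, function or pain medicine use. The Study Flow Chart records all three both at screening and after injection, and records satisfaction only after injection. The Screening Visit list is the only place where BMI is collected.

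On treatment effect, the Sample Size section assumes that "30% patients randomized to Lidocaine will avoid surgery compared to 70% of the patients randomized to Lidocaine with Dexamethasone". The Primary/Secondary Outcome Variables section lists disability (NDI), pain and satisfaction as secondary outcomes, the first two worded as decreases.

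**The concern.** A test of surgery avoidance against one variable cannot hold arm constant. If the steroid raises avoidance and also improves that variable, arm is a common cause of both. The pooled test can then show an association even where the variable has no relation to surgery within either arm. This component grows with the treatment effect, so it is largest in the situation for which the trial is powered. A reader of the results could not tell a patient-level signal from a restatement of the treatment effect.

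**Working it through.** **Inputs from the protocol.** Avoidance is 30% v 70% (Sample Size). Allocation is 1:1 (Treatment Groups). "With a level of significance of 0.05 and power of 80%, 23 patients are needed in each group", raised to 30 per group for attrition (Sample Size). The size of any steroid effect on the seven variables is not given, so d (in SD units) is an assumption and is shown as a range.

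**The plan's own figure.** Two-sided alpha is assumed, as the protocol does not state sidedness. With the pooled-variance formula, n = [1.96 × √(2 × 0.5 × 0.5) + 0.842 × √(0.3 × 0.7 + 0.7 × 0.3)]² / 0.4² = (1.386 + 0.545)² / 0.16 ≈ 23.3, which rounds up to 24. The arcsine formula gives 23.2. Power at 23 per group is 79.4%. The stated 23 is reproduced to within rounding.

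**Share of steroid patients by outcome.**
- Among those who avoid surgery: 0.5 × 0.7 / (0.5 × 0.7 + 0.5 × 0.3) = 0.70.
- Among those who have surgery: 0.5 × 0.3 / (0.5 × 0.3 + 0.5 × 0.7) = 0.30.

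**Difference created by pooling.** If the steroid shifts a variable by d SD and nothing links it to surgery within an arm, the expected difference (avoided minus surgery) is (0.70 − 0.30) × d = 0.4d. Mixing the arms makes the variance within each outcome group 1 + 0.7 × 0.3 × d², so the standardized difference is 0.4d / √(1 + 0.21d²): 0.195, 0.30 and 0.364 for d = 0.5, 0.8 and 1.0.

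**Rejection rates at 0.05 with no within-arm link** (40,000 simulated trials per setting; the adjusted test is a linear model containing arm):

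| Assumed steroid shift | Pooled t-test, 23 per arm | Pooled t-test, 30 per arm | With arm included |
|---|---|---|---|
| 0 SD | 5.2% | 5.1% | about 5% |
| 0.2 SD | 5.7% | 6.1% | about 5% |
| 0.5 SD | 10.2% | 11.6% | about 5% |
| 0.8 SD | 17.1% | 21.2% | about 5% |
| 1.0 SD | 22.8% | 28.8% | about 5% |
| 2.0 SD | 50.4% | 61.1% | about 5% |

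The adjusted rate lay between 4.9% and 5.2% throughout. With a logistic model and a likelihood-ratio test it was about 5% to 6%. A binary variable that the steroid moves from 30% to 70% gives a pooled chi-square rejection rate of 20.5% at 23 per arm and 24.7% at 30.

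**Hand check, d = 0.8 and 30 per arm.** About 30 patients fall in each outcome group, so the test statistic is centred near 0.30 × √(30/2) = 1.16. The chance of exceeding 1.96 is P(Z > 0.80) ≈ 21%, as simulated.

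**Variables fixed before injection.** Randomization makes these independent of arm apart from chance, so d = 0 and the pooled error rate stays at about 5%. Leaving out arm still costs power. For an assumed within-arm latent correlation of 0.4 with avoidance, including arm raises power from about 47% to 54% at 23 per arm and from about 58% to 66% at 30.

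**The case against.** The strongest objection is that the zero-link case conflicts with the protocol. The Primary Outcome Variables paragraph defines failure as surgery because the injections did not relieve pain and improve function. The sections on refusing the second and fourth injections provide for referral back to the surgeon when pain has risen or the patient is dissatisfied. For follow-up pain and satisfaction, some within-arm link is therefore built in. If the steroid prevents surgery entirely by relieving pain, the association is real. Under full mediation with an assumed 1.5 SD shift, the pooled test rejects in about 100% of trials and the arm-adjusted test in 98% to 99.5%, so adjustment changes almost no conclusion. This stands. In that case, including arm separates the within-arm association from the treatment effect; it does not remove a false positive.

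A reader might also infer that all seven tests are distorted. The documents do not support that. Age and gender cannot be changed by the steroid, BMI is collected only at screening, and pain, function and pain medicine use are exposed only if follow-up values are used. Satisfaction alone is exposed on any reading.

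Nor do the figures support saying that an affected variable will falsely appear as a predictor. At shifts of 0.5 to 1.0 SD a significant false result is a minority outcome, and the plan speaks of associations, not predictors.

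What remains is that no sentence in the plan lets the analyst or reader separate the two components.

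**Conclusion.** The point holds in limited form. For post-injection variables, the planned association combines the treatment effect with any patient-level link, and the treatment part is 0.4d SD in expectation. Where there is no within-arm link, the false-positive rate is about 10% to 23% at 23 per arm and 12% to 29% at 30 per arm for shifts of 0.5 to 1.0 SD, against a nominal 5%. For pre-injection variables there is no expected bias, only a loss of power of about 7 to 8 percentage points in the example.

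These sizes rest on the assumed shifts, on the 30% v 70% difference being real (with equal avoidance in the arms the effect vanishes), and on pooling, which is the natural reading but is not stated. A combined error rate over several variables would need further assumptions about how many are affected and how they correlate, so none is relied on here. The point concerns the association analyses and says nothing about the validity of the comparison between arms.

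**What to change.** In the Statistical analysis section:

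- Test each variable in a logistic model for surgery avoidance that contains randomized arm plus that one variable. For gender, a Cochran-Mantel-Haenszel test stratified by arm serves the same purpose.
- Report the arm-adjusted association with its 95% CI.
- State the time point of every variable. Use screening values for pain, function and pain medicine use.
- Label any post-injection variable, such as satisfaction, as descriptive.

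The cost is a change of wording and one degree of freedom per model; no new data are needed. One limit remains. The paragraph before Follow-up Office Visits ends effectiveness evaluations once a patient elects surgery, so later values are missing according to outcome. Adjusting for arm does not cure that, which is a further reason to rely on screening values and to keep post-injection associations descriptive.

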1. Subjects who have cervical radicular pain without significant neurologic deficit (neurologic deficit is defined as manual muscle testing less than 3/5), MRI/CT findings of neural compression (neural compression is defined as disc herniation or central or foraminal spinal stenosis),
2. Failed 6 weeks of conservative treatment (conservative treatment is defined as relative rest, home exercise, physical therapy, and use of anti-inflammatory and/or analgesic medications),
3. Deemed to be good operative candidates by spine surgeons (patients with MRI/CT findings of neural compression with concordant symptoms) and had agreed to possible operative intervention

Exclusion Criteria:

1. History of
 - a. acute trauma,
 - b. diabetic neuropathy,
 - c. active infection,
2. Active progressive neurological deficit (neurologic is deficit defined as manual muscle testing less than 3/5),
3. Medical condition that may affect the cervical spine neurological exam and/or pain assessment (e.g. peripheral neuropathy),
4. More than one cervical level requiring injection,
5. Previous cervical fusion surgery,
6. Bleeding disorders or other medical contraindications to the injection procedure,
7. Absence of substantial radicular pain (radicular pain is defined as arm pain greater than neck pain),
8. Involvement in workers' compensation claim, or any litigation related to neck injury.
9. Patients who are pregnant, or who plan to become pregnant in the next 12 months

Data Collection and Treatment Administration

Data Collection

Screening Visit

The primary operator or blinded investigator and/or designee will screen patients for potential participation in the study. The following data points will be collected for all patients:

- Informed Consent
- Patient demographics (medical record number, age, gender, ethnicity, body mass index (BMI),

- Patient medical history (smoking history, acute trauma, diabetes (type I or type II), active infection, active progressive neurological deficit, bilateral disease, bleeding disorders or other medical contraindications to the injection procedure, presence of radicular pain)
- NDI questionnaire (disease specific measure), Verbal Numeric Pain Score, Pain Medication Use, and Neurological Exam

Blinding

This is a double-blind study (i.e., the patient and the blinded investigator are both unaware of the specific study treatment being administered).

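### The Statistical analysis section plans no baseline-adjusted between-arm analysis of NDI, neck pain or radicular pain, although NDI and pain are scored at screening

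*Combined protocol and SAP*

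**What the plan says.** Primary/Secondary Outcome Variables words the secondary outcomes as reductions. For pain the text is "Decreased neck pain and radicular pain as measured by a numerical pain rating", and the NDI item is phrased in the same way. Change from baseline is not defined.

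The Screening Visit list includes "NDI questionnaire (disease specific measure), Verbal Numeric Pain Score, Pain Medication Use, and Neurological Exam". Follow-up Office Visits and the Study Flow Chart repeat NDI and the pain score at 4 weeks, 12 weeks, 6 months and 12 months.

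The Statistical analysis section is one paragraph. It opens with "Normality testing will be conducted for all continuous variables" and uses the result to choose between mean with SD and median with interquartile range. It continues: "Bivariate analyses will be conducted to determine the associations between surgery avoidance and age, gender, pain, function, pain medicine consumption, BMI and subject satisfaction". The next and last sentence is "Chi-Square tests will be used for categorical data and t-test or the nonparametric equivalent will be used for continuous data". The section names no covariate, regression, ANCOVA, repeated-measures model or key visit. No sentence states a comparison of NDI or pain between the two arms.

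The text just before Follow-up Office Visits adds: "Patients who elect to undergo surgery will be discontinued from the study and no further effectiveness evaluations will be performed".

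**The concern.** A screening score is available for outcomes that will be compared in at most 30 patients per arm, and nothing in the plan says it will be used as a covariate. If the last sentence of the section is the between-arm test, that test is less precise than one the existing data already support. If it is not, the plan names no between-arm test for NDI or pain at all.

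The analyst would also settle value or change, visit and test after seeing the data. At stake are the precision and credibility of the secondary comparisons, not the primary result.

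**Working it through.** **The plan's own figure.** Sample Size states "With a level of significance of 0.05 and power of 80%, 23 patients are needed in each group", for surgery avoidance of 30% against 70%. With a two-sided 0.05 level (sidedness is not stated) and pooled variance:

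n = [1.960 × √(2 × 0.5 × 0.5) + 0.842 × √(0.3 × 0.7 + 0.7 × 0.3)]² / 0.4² = (1.386 + 0.545)² / 0.16 = 23.3

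This is 24 when rounded up; the arcsine formula gives 23.2. The stated 23 is reproduced to within one patient. It concerns a binary outcome and does not depend on how NDI and pain are analysed.

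**Inputs for NDI and pain.** The 30 per arm is from Sample Size. The correlation r between screening and follow-up scores, and the true difference of 0.6 SD, are assumptions. I use r = 0.3, 0.5 and 0.7, equal SDs at both times, and two-sided 0.05.

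**Variance relative to a t-test on follow-up values (= 1):**

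- t-test on change: 2(1 − r)
- ANCOVA: 1 − r²
- ANCOVA relative to change: (1 − r²) / [2(1 − r)] = (1 + r)/2

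| r | Variance, change | Variance, ANCOVA | SE, ANCOVA / follow-up = √(1 − r²) | SE, ANCOVA / change = √((1 + r)/2) |
|---|---|---|---|---|
| 0.3 | 1.40 | 0.91 | 0.95 | 0.81 |
| 0.5 | 1.00 | 0.75 | 0.87 | 0.87 |
| 0.7 | 0.60 | 0.51 | 0.71 | 0.92 |

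ANCOVA has the smaller standard error in every row. Which t-test is the better one depends on r: at 0.3 the change score is worse than ignoring baseline, at 0.5 they tie, and at 0.7 it is better. Leaving value or change unstated therefore matters.

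**Power at 30 per arm, difference 0.6 SD.** The effective standardised difference is 0.6 divided by the square root of the relative variance, entered in a two-sample t-test calculation. For ANCOVA this gives 0.6/0.954 = 0.63, 0.6/0.866 = 0.69 and 0.6/0.714 = 0.84.

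| r | t-test, follow-up | t-test, change | ANCOVA |
|---|---|---|---|
| 0.3 | 63% | 49% | 67% |
| 0.5 | 63% | 63% | 75% |
| 0.7 | 63% | 84% | 89% |

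**Fewer patients.** Attrition of 30% leaves 30 × 0.7 = 21 per arm. Power is then 48% for the follow-up t-test and 51%, 59% and 76% for ANCOVA.

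Scores also stop at surgery. At the planning rates and with no other loss, 30 × 0.3 = 9 and 30 × 0.7 = 21 patients would still be unoperated at 12 months. Power is then about 31% for the follow-up t-test and 39% for ANCOVA at r = 0.5. Those 9 and 21 are a subset selected by outcome, so the comparison is no longer of the randomised groups.

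**The case against.** Several objections have force.

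- A reader might infer that NDI and pain would be compared without their baseline values. The documents do not establish this. The outcomes are worded as decreases, which fits a t-test on change, and a change score uses the baseline, though less efficiently than ANCOVA.
- The sentence on tests directly follows the associations with surgery avoidance and may describe only those. This stands. On that reading the gap is wider, because no between-arm analysis is specified.
- A reader might infer that a normality test selects the method. The section ties normality explicitly only to descriptive summaries. Its use to choose between the t-test and the nonparametric equivalent is a fair inference, but it is not stated.
- The contrast of 63% with 89% takes the follow-up-only reading, the highest assumed correlation and 30 per arm. At r = 0.3 the gain over that test is 4 points, and at r = 0.7 the gain over a change score is 5 points.
- Multiplicity might be pressed as well. Four outcomes (NDI, neck pain, radicular pain, satisfaction) at four visits give 16 tests, and 1 − 0.95¹⁶ = 56% if they were independent, less if correlated. These are secondary outcomes with no stated confirmatory claim, and one visit each still leaves 1 − 0.95⁴ = 18.5%. This is a side matter.
- Loss of scores after surgery is a larger threat to the later visits than lost precision. That is true, and neither baseline adjustment nor a mixed model removes it.

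None of this supplies the missing specification or makes either t-test as precise as ANCOVA at the correlations tried.

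**Conclusion.** The concern holds in a limited form: no baseline-adjusted between-arm analysis of NDI, neck pain or radicular pain is planned, and the plan leaves open whether values or changes are tested and at which visit. The direction of the precision gain is the same on either reading. Its size is not known from the documents. Over r = 0.3 to 0.7, the standard error falls by 5% to 29% against a follow-up t-test, and by 19% to 8% against a change-score t-test. The power figures also rest on the assumed 0.6 SD and on 30 scored patients per arm, and are lower once patients leave.

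This should be corrected, but it is not a flaw in the primary analysis. The documents do not support the stronger statement that baseline data would be discarded, nor any single figure for the power lost.

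**What to change.** In Statistical analysis:

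- State that NDI, neck pain and radicular pain are each compared between arms by ANCOVA at one named visit, with the screening score as covariate. A repeated-measures model with the same covariate is an alternative.
- Report the adjusted mean difference with its 95% CI, and treat the other visits as supportive.
- Keep a rank analysis as a sensitivity check, and say that normality testing does not choose the method.
- Say whether the sentence on chi-square and t-tests covers the surgery-avoidance associations, the arm comparisons, or both.
- State that scores end at surgery, so that a later comparison is either in a selected subset or assumes that post-surgery scores are missing at random, and that baseline adjustment does not remove this.

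The cost is plan wording, a little programming and one degree of freedom for the baseline covariate. A repeated-measures model uses more parameters: visit, arm-by-visit and covariance terms (10 if unstructured over four visits). With at most 60 patients and falling numbers, ANCOVA at one visit is the lighter choice. No extra visits or patients are needed.
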